Test days: Each subject will be scheduled for two different visits at the Yale PET Center, separated by at least six days (based on the duration of calcitriol's pharmacological activity of 3-5 days) (Table 1). Each test day will start approximately at 8:00 am with verification that subjects were fasting (e.g., "NPO") since 11:59 pm the night before, followed by measurement of vital signs, an electrocardiogram, rapid dipstick urinary pregnancy test, and a blood draw of 10 milliliters (ml) to measure serum 1-25 (OH)₂ D₃ and calcium levels. Afterwards subjects will have oral administration of the study medication (e.g., three 0.5 mcg capsules of calcitriol vs. placebo). Thirty-five minutes after administration of the study medication, subjects will complete two different brief self-ratings: The Drug Effects Questionnaires and the Simplified Version of the Amphetamine Interview Rating Scale (Van Kammen and Murphy 1975, Morean, de Wit et al. 2013). Before the baseline scan, subjects will complete the eye blink rate and the Probabilistic Reversal Learning Task (PRLT).

Preparation of the subject for PET scanning will include the placement of a venous line. The purpose of the venous line is for the [¹¹C]-PHNO injection; the venous line may also be used for blood sampling. Approximately two hours (i.e., 120 minutes) after calcitriol administration, subjects will have IV administration of a dose of up to 10 mCi of [¹¹C]-PHNO. Then each subject will undergo a 120-minute dynamic (i.e., emission and transmission) scan on a high-resolution research tomography (HRRT). Ninety minutes after starting the [¹¹C]-PHNO PET scan, subjects will have blood drawn for measurement of calcitriol levels. Upon completion of the [¹¹C]-PHNO PET scan, subjects will complete a 20-minute, computer-based task of attention, the CPT-IP (i.e. continuous performance task). Approximately 4.5 hours after receiving the study medication, subjects will receive an oral dose of dextro-amphetamine (Dexedrine 0.3 mg/kg, to a maximum dose of 30 mg). Subjects will have blood drawn for the measurement of amphetamine levels at 60 and 120 minutes after receiving dextro-amphetamine. Before the second scan, subjects will complete the eye blink rate. Approximately two and a half hours after receiving dextro-

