If participating as an inpatient, ADHD subjects will follow the same MRI procedures, study procedures night before each experiment day, and test day procedures, with the main variation being that they will be admitted to the CNRU while they complete those. The CNRU is an inpatient, research dedicated, research unit, staffed 24 X 7 with medical and nursing staff, where visitors are screening/restricted. Upon admission to CNRU, subjects will conduct admission procedures including medical and psychiatric examination, blood work for CBC with differential, comprehensive metabolic panel with TSH and serum pregnancy test, urinalysis, ECG, and urine toxicology. The total length of stay on the CNRU will be up to 3 weeks depending on days needed to complete 5 half lives off stimulant medications and depending on slots for PET imaging scan which will be scheduled at least 6 days apart from each other. The first days on the CNRU are meant to acclimatized to the inpatient environment. Congruent with inpatient study procedures: they will not need to receive study medication to take home after MRI; they don't need to have administration of study medication monitored by Skype/Facetime; compliance with dietary measurements before test days is supervised by staff from CNRU; and they will be returning from the PET Imaging Center back to the CNRU after completion of each test day.

Follow up: The day after completion of each test day, subjects will be asked to return to the CNRU for a blood draw in order to measure calcium levels. The amount of blood drawn will be less than 5 ml. The purpose of this procedure is to monitor the development of hypercalcemia as an adverse event. In addition, a study physician will interview subjects in order to assess any potential residual side effects relative to their pre-scan baseline. At the end of the first follow up visit, subjects will receive 3 capsules of the study medication (i.e., each capsule will have calcitriol 0.5 mcg or placebo) as well as another instruction sheet for the second experimental day. The second experimental day is the same as the first one.

ADHD outpatient subjects will complete the same follow up. Inpatient subjects, because they are residing on the CNRU during those days, don't need to receive either the study medication or instructions for the next experiment day, as part of their follow up.

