Dosing: We will use a threshold Dexedrine dose of 0.3 mg/kg (as oppose to 0.4 mg/kg or 0.5 mg/kg in order to minimize the potential for ceiling effects on DA release/[¹¹C]-PHNO displacement, thereby maximizing the chances of detecting calcitriol related augmentation of stimulant-induced DA release.

The choice of calcitriol dose (3 mcg) is based on previous studies in both rodents and humans (Broadus, Erickson et al. 1984, Erickson, Cooper et al. 1984, Bianchi, Ardissino et al. 1999, Brandi, Egfjord et al. 2002, Beer, Eilers et al. 2003, Beer, Ryan et al. 2007, Cass, Peters et al. 2012). Such studies have employed higher doses than physiologic ones (i.e., those employed in the treatment of vitamin D deficiency) and have demonstrated the safety of oral doses as high as 0.5 mcg/kg (among persons with malignancies) (Beer, Lemmon et al. 2003) or oral/IV doses as high as 4 mcg (among healthy controls) (Brandi, Egfjord et al. 2002). Studies in healthy controls (N=11) using a protocol of 3 mcg of daily oral calcitriol for 10 consecutive days (Broadus, Erickson et al. 1984) have been shown to be safe and well-tolerated, with a single subject developing mild hypercalcemia after six days (this subjects continued in the study at a reduced dose of 1.5 mcg per day without complications). In the current study, the total dose of 3 mcg will be divided in two separate administrations of 1.5 mcg for ease of administration (e.g., three capsules will be easier than six), to maximize chances that [¹¹C]-PHNO scans are conducted after calcitriol has had sufficient time to take effect (e.g., onset of action after 2 hours; maximum effect after 10 hours; duration of effect is 3 to 5 days), and to maximize chances of subjects tolerating it/minimizing chances of any adverse events.

Doses of calcitriol and Dexedrine (if applicable) administered to ADHD subjects are the same ones as the ones administered to healthy controls. ADHD outpatient subjects will take the normal, prescribed dose of their prescription stimulant medication.

Table 1. Timeline of Study Procedures ^

Study Procedure	Night Before Day 1	Day 1	Night Before Day 2	Day 2	Time Relative to Scan #1	Time Relative to Scan #2
Pretreatment Dose 1 (Placebo vs. Calcitriol)	✓		✓			- 18 hr
Baseline Vital Signs		✓		✓	- 130 min	
ECG and Blood Draw (Calcitriol and Ca ²⁺)		✓		✓	- 125 min	
Pretreatment Dose 2 (Placebo vs. Calcitriol)		✓		✓	- 120 min	- 7 hr
Self-Ratings (DEQ and AIRS*)		✓		✓	- 90 min (and Q45 min thereafter)	

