10.5. Risks of calcitriol administration: Subjects will be asked to withhold any supplemental calcium intake, as well as to decrease consumption of foods rich in calcium content (e.g. dairy products, foods with milk or milk products as a main ingredient, high-calcium vegetables, legumes, and seafood starting 24 hours prior to each test day until 48 hours after. They will be asked to drink 3-4 cups (24-32 ounces) of water or electrolyte containing fluids above their usual intake starting 12 hours before the dose. This oral hydration will be recommended for 3 days after dosing (Beer, Munar et al. 2001, Beer, Javle et al. 2007). Based on literature reviewed, it is not expected for subjects to have hypercalcemia but if they develop it, it is expected for it to be asymptomatic and to resolve spontaneously without the need for treatment. Notwithstanding the above, subjects will be educated about these symptoms (i.e. polyuria, polydipsia, nausea, vomiting, constipation). Serum calcium levels will be measured each experiment day, as well as the day after each experiment day, in order to detect asymptomatic cases of mild hypercalcemia. The study will be discontinued if the calcium levels are congruent with mild hypercalcemia or higher than 11.5 mg/dL. In these cases we will arrange for consultation with internal medicine specialists.

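### Scheduled calcium and side-effect checks stop the day after each test day, inside the protocol's own 3-5 day calcitriol effect, and subjects given calcitriol second have no later check.

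*Combined protocol and SAP*

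**What the plan says.** - **Follow-up visit (Section V.3, Follow up).** "The day after completion of each test day, subjects will be asked to return to the CNRU for a blood draw". The reason is explicit: "The purpose of this procedure is to monitor the development of hypercalcemia as an adverse event". At the same visit "a study physician will interview subjects in order to assess any potential residual side effects relative to their pre-scan baseline". Section V.10.5 gives the same calcium schedule (each test day and the day after), and Section V.10.6 places the interview at the same session. I find no later draw, visit or call after the second follow-up.
- **Duration of effect.** Section V.3 (Test days) sets the gap between test days at six days or more, "based on the duration of calcitriol's pharmacological activity of 3-5 days". Section V.3 (Dosing) gives the time course as "onset of action after 2 hours; maximum effect after 10 hours; duration of effect is 3 to 5 days", and the calcitriol background in Section VI.A repeats it.
- **Precautions (Section V.10.5).** Calcium intake is restricted "starting 24 hours prior to each test day until 48 hours after". On extra fluids: "This oral hydration will be recommended for 3 days after dosing". The section expects any hypercalcemia to be asymptomatic and to resolve without treatment, and says the calcium draws are there to find asymptomatic mild cases.
- **Passive route.** Subjects are taught the symptoms (V.10.5), are given the study physicians' phone numbers and are asked to call about side effects, with no end date (V.10.6). The principal investigator reviews all adverse events when each subject completes (V.11, item 7).

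**The concern.** The protocol treats calcitriol as active for days when it separates the two test days and when it instructs subjects on diet and fluids. It schedules safety ascertainment for only one day after. No reason is given for the shorter period.

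Two things are at stake. First, hypercalcemia that appears or persists after the next-day visit, in the asymptomatic form the protocol expects, would not be found in a subject whose calcitriol came last. Second, a report of no hypercalcemia would be read as covering the drug's effect, when it describes roughly the first day after the last dose, with diet and fluid precautions in force. The effect on binding potential, the primary outcome, is not touched.

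**Working it through.** The plan states no coverage figure, so there is none to reproduce. The check is a timeline with time zero at the second pretreatment dose (about 8 am on the test day).

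**Inputs**
- Table 1: dose 1 is 18 h and dose 2 is 7 h before scan 2. The interval is 18 - 7 = 11 h, which agrees with 9 pm to 8 am.
- Table 1: calcium is drawn just before dose 2 and 90 min into scan 2.
- Follow-up draw: the next day. Assumption: between 8 am and 5 pm.
- Stated effect: 3-5 days, or 72-120 h, counted from dose 2.
- Section V.3 (PET imaging): a test day may run from 8 am to 5 pm.

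**When calcium is measured**
- Test-day draw: 7 + 1.5 = 8.5 h after dose 2, and 8.5 + 11 = 19.5 h after dose 1.
- Next-day draw: 24 h (8 am) to 24 + 9 = 33 h (5 pm) after dose 2.
- The stated maximum at 10 h lies between these two draws.

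**Stated effect left without a scheduled check**

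| Stated duration | Draw at 24 h | Draw at 33 h |
|---|---|---|
| 72 h | 72 - 24 = 48 h | 72 - 33 = 39 h |
| 120 h | 120 - 24 = 96 h | 120 - 33 = 87 h |

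The range is 39-96 h, roughly two to four days.

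**Precautions against the last draw**
- Diet: the restriction runs to 48 h after the test day, so with a 5 pm finish it ends 9 + 48 = 57 h after dose 2. Stated effect remaining on unrestricted diet: 72 - 57 = 15 h to 120 - 57 = 63 h.
- Fluids: 3 days is 72 h after dose 2, which covers the whole 3-day case and leaves 120 - 72 = 48 h of the 5-day case.
- Both precautions are still running at the 24-33 h draw.

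**By treatment order**
- *Calcitriol first.* The next calcium is the pre-dose draw on test day 2, at least 6 x 24 = 144 h after the calcitriol dose 2 (less a few minutes). The evening dose before it is placebo. Another calcium follows during scan 2, then the second follow-up draw and interview. The interval up to 120 h is unsampled, but there is a later check free of new calcitriol.
- *Calcitriol second.* Nothing is scheduled after the next-day visit. If allocation is 1:1 and all subjects complete, this is 30 / 2 = 15 per cohort. Section V.3 says only that the first day is randomly assigned.
- *Placebo first.* The gap after test day 1 carries no calcitriol exposure.

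**The case against.** The strongest reply is that the schedule watches the period that matters. Calcium is measured on both sides of the stated 10 h maximum, so the unsampled time is the declining part of the effect. The 3-5 day figure is used to justify washout, not toxicity monitoring. Subjects are screened on calcium, phosphate, renal function and stones, and they have a number to call. Inpatients are on a unit staffed around the clock between test days.

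Much of this stands, and it rules out several stronger readings that a reader might infer:
- **That late hypercalcemia would never be reported.** Symptomatic events have a passive route through the request to call and the adverse-event review. What is missing is scheduled, active ascertainment.
- **That most of the risk is unmonitored.** The draw reaches 24/120 = 20% to 33/72 = 46% of the stated hours, but share of hours is not share of risk when the effect is declining.
- **That the calcium discontinuation rule is disabled.** After test day 2 no study dose remains to stop. For a calcitriol-first subject the remaining pretreatment is placebo.
- **That a case on day 6 in a cited healthy-volunteer study shows late onset.** That study dosed daily for 10 days, so it says nothing about onset after a single 3 mcg exposure.

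The reply does not close the gap. The call route depends on symptoms, while Section V.10.5 expects none. The 10 h figure is a maximum of effect; the protocol does not say that serum calcium peaks then. The end-of-participation review can consider only events that were ascertained.

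**Conclusion.** The concern holds in limited form. After a final test day on calcitriol, about 39-96 h of the protocol's own stated effect has no scheduled calcium and no active contact. Calcitriol-first subjects are seen again, so ascertainment after calcitriol depends on treatment order, and an incidence pooled over both orders mixes two lengths of observation.

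The size rests on three assumptions: a follow-up visit between 8 am and 5 pm, the 3-5 days counted from dose 2, and, for the statement that about half are affected, 1:1 allocation. The documents do not show that late hypercalcemia is likely after this exposure, and the efficacy analysis is unaffected. This is an inexpensive improvement to safety ascertainment and to the accuracy of the safety report.

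**What to change.** 1. Reconcile the follow-up in Section V.3 and the precautions in Section V.10.5 with the duration of effect in Section V.3 (Test days and Dosing) and Section VI.A. Otherwise, state why the next-day cut-off is sufficient.
2. Extend adverse-event ascertainment over the protocol's own stated window after the final test day. Existing staff can do this by the phone or video contact already in use. For inpatients still on the unit, record events over the same window.
3. Leave the timing of any further calcium measurement to the clinical team. A symptom call will not detect asymptomatic cases, so the reconciliation should address that limit openly.
4. Report calcium results as covering about the first 24-33 h after the last dose, under diet and fluid precautions. Show the later values in calcitriol-first subjects separately, by treatment order.

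The cost is protocol wording and one short call per subject. No additional visit is needed.

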Yes (provide a description of that interest in a separate letter addressed to the HIC)
 No

I assure the HIC that the principal investigator and all members of the research team are qualified by education, training, licensure and/or experience to assume participation in the conduct of this research trial. I also assure that the principal investigator has departmental support and sufficient resources to conduct this trial appropriately.

Chair Name (PRINT) and Signature _____

Date _____

Department _____

YNHH Human Subjects Protection Administrator Assurance Statement

Required when the study is conducted solely at YNHH by YNHH health care providers.

As Human Subject Protection Administrator (HSPA) for YNHH, I certify that:

- I have read a copy of the protocol and approve it being conducted at YNHH.
- I agree to notify the IRB if I am aware of any real or apparent institutional conflict of interest.
- The principal investigator of this study is qualified to serve as P.I. and has the support of the hospital for this research project.

YNHH HSPA Name (PRINT) and Signature _____

Date _____

SECTION V: RESEARCH PLAN

1. **Statement of Purpose:** State the scientific aim(s) of the study, or the hypotheses to be tested.

Specific Aim 1: As part of a within-subject, two-days, study design, to determine whether acute calcitriol (vs. placebo) pre-treatment is associated with greater amphetamine (Amp)-induced dopamine (DA) release in the caudate, putamen, ventral striatum (VST), and substantia nigra / ventral tegmental area (SN/VTA) of healthy human subjects. **Hypothesis:** Given prior evidence of increased amphetamine-evoked DA release in rats pretreated with calcitriol compared to placebo (Cass, Peters et al. 2012), we hypothesize that pre-treatment with calcitriol will produce greater Amp-induced DA release relative to placebo, resulting in lower post-Amp, [¹¹C]-PHNO BP_{ND} values on calcitriol as compared to placebo days. If confirmed, such data would provide compelling preliminary support for the adjunctive use of calcitriol for enhancing stimulant medication effects (leading to larger scale PET imaging and/or clinical trial studies in humans with Attention Deficit Hyperactivity Disorder or ADHD).

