Specific Aim 2: To determine whether acute calcitriol (vs. placebo) pre-treatment is associated with better performance on a test of attention (e.g., the continuous Performance Task or CPT–IP), after treatment with amphetamine. **Hypothesis:** We hypothesize that healthy human subjects pre-treated with calcitriol will have faster reaction times/higher accuracy on the CPT–IP vs. subjects pre-treated with placebo, after treatment with amphetamine.

Specific Aim 3: As part of a within-subject, two-days, study design, to determine whether acute calcitriol (vs. placebo) pre-treatment is associated with greater amphetamine (Amp)-induced dopamine (DA) release in the caudate, putamen, ventral striatum (VST), and substantia nigra / ventral tegmental area (SN/VTA) of subjects with attention deficit hyperactivity disorder (ADHD). **Hypothesis:** Similar to our hypothesis with healthy controls and congruent with our preliminary findings, we hypothesize that pre-treatment with calcitriol will produce greater Amp-induced DA release relative to placebo, resulting in lower post-Amp, [¹¹C]-PHNO BP_{ND} values on calcitriol as compared to placebo days.

Specific Aim 4: To determine whether acute calcitriol (vs. placebo) pre-treatment is associated with better performance on a test of attention (e.g., the continuous Performance Task or CPT–IP), after treatment with amphetamine. **Hypothesis:** Similar to our hypothesis with healthy controls and congruent with our preliminary findings, we hypothesize that individuals with ADHD pre-treated with calcitriol will have faster reaction times/higher accuracy on the CPT–IP vs. subjects pre-treated with placebo, after treatment with amphetamine
2. **Background:** Describe the background information that led to the plan for this project. Provide references to support the expectation of obtaining useful scientific data.

[figure not shown]

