PET imaging: PET scans are acquired as subjects rest on a high-resolution research tomography HRRT (207 slices, with a 1.2 mm slice separation and a reconstructed image resolution of ~3 mm). This resolution permits visualization of [¹¹C]-PHNO uptake in the caudate, putamen, ventral striatum (VST), and substantia nigra / ventral tegmental area (SN/VTA). Partial immobilization of the head will be done using Velcro strips and Coban. In addition, on the HRRT scanner, a sensor will be attached to the Coban on the subject's head which will allow for tracking and correction of any head movement during the scan. An attenuation correction scan is obtained immediately before or after each emission scan.

The PET scans will be acquired using i.v. bolus administration of 10 mCi dose of high-specific activity [¹¹C]-PHNO (maximum mass dose of 0.03 µg/kg) as described by Gallezot and colleagues (Gallezot, Beaver et al. 2012). Each dynamic PET scan will last up to 120 minutes (including attenuation correction and emission scan). Subjects will be asked to void immediately after the scan is completed, to reduce radiation exposure to the bladder. Each experimental day may last from 8 am to 5 pm.

The primary outcome of DA displacement will be post-Amp BP_{ND} in comparison to baseline BP_{ND}. We will conduct baseline scans on both days in order to rule out potential effects of calcitriol on D2/3 BP_{ND}.

ADHD subjects will complete same PET imaging study procedures as healthy controls.

Continuous Performance Task (CPT-IP): The Continuous Performance Task is one of the most widely used tests to quantify attention deficits and attentional changes induced by pharmacological agents in both clinical and research settings. It is a modified version of the older CPT-AX, giving it higher sensitivity to detect more subtle changes as well as also measuring working memory (Rapisarda et al. 2014) (Cornblatt et al. 1988). In this computer based test the subjects are shown a random sequence of different numbers and are instructed to press a button as quickly and accurately as possible (with their preferred hand) upon detection of two identical pairs of numbers, and to withhold their response to any other sequence of letters. In order to ensure appropriate completion of the task, subjects will complete the task while video conferencing with research team using zoom, allowing virtual sharing of the screen.

ADHD subjects will also complete CPT-IP.

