Data Analysis: The PET image sets are aligned and re-sliced to yield images in the same planes and spatial system as the MRI images using AAL template. A number of modeling approaches will be taken to quantitate binding potentials (BP_{ND}). Initially, the primary focus will be on reference region approaches, specifically the Simplified Reference Tissue Models (SRTM); i.e., time-activity curves will be fitted with the Simplified reference tissue model to extract binding potentials (BP_{ND}) in various brain regions.

Data Analyses: The primary outcome will be non-displaceable tracer binding potentials ($BP_{ND} = V_T - V_{REF} / V_{REF}$), which are linearly proportional to the density of available $D_{2/3}$ Rs, computed using a simplified reference tissue model (SRTM) utilizing the cerebellum as a reference region. This method has been previously validated. PET data will be reconstructed into images at Yale PET Center with all standard corrections using the appropriate reconstruction protocols and filters. All PET data will be reconstructed with an iterative reconstruction algorithm, MOLAR, designed specifically for the HRRT. MOLAR incorporates attenuation, scatter and deadtime, and subject-motion (detected by the Vicra system), into the forward projection model for the scanner. Emission images are binned into equal frame times (typically 3 minutes). Following image reconstruction, an early summed image (0-12 min) will be registered to the subject's MR image, which will be registered to an MR template so PET can be transformed to a standard (MNI) space. HYPR filtering will be applied to all emission data before analysis. Regions of interest will be the caudate, putamen, ventral striatum (VST), and substantia nigra / ventral tegmental area (SN/VTA). We will perform within-subject comparisons of the relative change in BP_{ND} elicited by calcitriol + Amp vs. placebo + Amp (ΔBP_{ND}), using appropriate parametric (paired t-) or non-parametric (Wilcoxon signed-rank test) tests. Although the proposed sample will enable detection of significant differences of moderate effect sizes ($d' = 0.59$) with a power of 0.8 and two-tailed alpha of 0.05, the sample will, at a minimum, provide estimates of effect size/power upon which future larger scales studies may be based. This effect size is congruent with preclinical work (Cass, Peters et al. 2012) and with clinical [^{11}C]-(+)-PHNO and [^{11}C]

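### Aims 1 and 3 each span four unranked brain regions with no rule for deciding the aim, so the stated alpha and power hold region by region but not for a verdict on the aim

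*Combined protocol and SAP*

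**What the plan says.** Section V.1 states Aim 1 as a question about dopamine "release in the caudate, putamen, ventral striatum (VST), and substantia nigra / ventral tegmental area (SN/VTA) of healthy human subjects", and Aim 3 asks the same of the ADHD cohort. Each has one directional hypothesis; for Aim 1, "we hypothesize that pre-treatment with calcitriol will produce greater Amp-induced DA release relative to placebo". Neither aim ranks the four regions.

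Section V.12 repeats the list ("Regions of interest will be the caudate, putamen, ventral striatum (VST), and substantia nigra / ventral tegmental area (SN/VTA") and plans "within-subject comparisons of the relative change in BP_{ND} elicited by calcitriol + Amp vs. placebo + Amp", "using appropriate parametric (paired t-) or non-parametric (Wilcoxon signed-rank test) tests". The only alpha in the plan is in the power sentence, which says the sample will "enable detection of significant differences of moderate effect sizes ($d' = 0.59$) with a power of 0.8 and two-tailed alpha of 0.05". That sentence names neither a region nor an N. Its second half adds that the sample would in any case supply effect-size estimates for larger studies. The section closes by applying the same analyses to the ADHD cohort.

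Enrolment is 30 per cohort (Section VII.1). Section V.5 says this number allows for losses and technical failures but does not quantify them. The pilot data in Section V.2 come from two healthy subjects. They feature the ventral striatum and report similar findings in caudate, putamen and pallidum, but the plan does not make any region primary.

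**The concern.** Four regional results will exist per cohort, and the plan does not say how they combine into an answer to the aim. Section V.1 says that confirmation in healthy subjects would support larger imaging or clinical studies in ADHD, yet nothing defines what counts as confirmed. As written, an aim could be called supported on whichever of four tests at 0.05 is positive, or not supported because one of the four missed. Those two rules have different error rates and different power, and the single power line describes neither. A choice made after the four results are seen cannot be repaired later.

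**Working it through.** **Inputs.** From Section V.12: d=0.59, power 0.80, two-sided alpha 0.05, paired comparison, four regions. From Section VII.1: 30 enrolled per cohort. Not given: evaluable n and inter-region correlation ρ. I take n=25 (back-solved below) and n=30, and ρ from 0 to 0.95, equal for all pairs.

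**1. The plan's own figure.** For one paired t-test, the noncentrality is d√n and power is P(T′ > t₀.₉₇₅,ₙ₋₁), with T′ noncentral t on n−1 degrees of freedom.

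| n | d√n | critical t | power at d=0.59 | detectable d at 80% |
|---|---|---|---|---|
| 24 | 2.890 | 2.069 | 0.790 | 0.597 |
| 25 | 2.950 | 2.064 | 0.808 | 0.584 |
| 26 | 3.008 | 2.060 | 0.824 | 0.572 |
| 30 | 3.232 | 2.045 | 0.878 | 0.529 |

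So 0.59 fits one region with about 24 to 26 evaluable subjects; 25 of 30 would be a loss of 5/30 = 17%. With the Wilcoxon test and normal differences, simulated power is 0.787 at n=25 and 0.806 at n=26. At all 30 the line is conservative.

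**2. Any one region counts, no true effect anywhere.** The nominal rate in the hypothesised direction is 0.05/2 = 2.5%. At ρ=0 the rate over four regions is 1 − 0.975⁴ = 9.6%. Counting either direction, it is 1 − 0.95⁴ = 18.5%. Other values of ρ were simulated (200,000 replicates, four equally correlated normal differences).

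**3. All four must be positive.** False support is 0% to 1.3% if all four are null, and at most 2.5% if any one is null. Power was simulated with d=0.59 in every region.

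**4. Candidate rules.** Column A is false support under the any-region rule, in the hypothesised direction, at n=25. B is power when all four must be positive. C is the chance of at least one positive region with Holm over all four. D is average power per secondary region with Holm over three, tested only if the primary region is significant. B, C and D are given as n=25 / n=30.

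| ρ | A | B | C | D |
|---|---|---|---|---|
| 0 | 9.6% | 0.43 / 0.59 | 0.98 / 0.99 | 0.61 / 0.74 |
| 0.5 | 7.9% | 0.56 / 0.69 | 0.88 / 0.94 | 0.65 / 0.76 |
| 0.8 | 5.8% | 0.66 / 0.77 | 0.79 / 0.87 | 0.68 / 0.79 |
| 0.9 | 4.8% | 0.71 / 0.80 | 0.73 / 0.82 | 0.70 / 0.79 |
| 0.95 | 4.0% | 0.74 / 0.83 | 0.70 / 0.79 | 0.70 / 0.79 |

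Column D at ρ=0 can be checked by hand. Unconditional Holm-over-three power is 0.751 (n=25) and 0.847 (n=30), so 0.808 × 0.751 = 0.61 and 0.878 × 0.847 = 0.74. Holm over four holds false support in the hypothesised direction to 2.5% (ρ=0) down to 1.1% (ρ=0.95). A single named primary region has 2.5% false support and power 0.81 / 0.88 at any ρ.

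**The case against.** The strongest reply is that the plan may intend four separate regional results with no overall verdict. Each region then has its own 5% error rate and roughly its own 0.80 power, and the power sentence fits as written. That stands as a defence of the figure. It does not say how the single hypothesis in each aim would be judged.

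Second, the study is preliminary, and Section V.12 falls back on estimation. This lowers the stakes. But the same sentence claims power to detect significant differences, and Section V.1 speaks of confirmation.

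Third, all four regions come from the same scans with one cerebellar reference, so zero correlation is hard to defend. I agree: the 4% to 6% range is the more realistic one. The 18.5% figure also counts effects opposite to the hypothesis and should not be the headline.

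Fourth, naming one region is not the only sound rule. This also stands. Holm over all four controls error and at 30 subjects nearly keeps 0.80 throughout.

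A reader might also infer that the documents name two different primary endpoints, because the PET imaging text in Section V.3 says "The primary outcome of DA displacement will be post-Amp BP_{ND} in comparison to baseline BP_{ND}" while Section V.12 calls BP_ND primary and compares its relative change. The documents do not support this. Section V.2 defines ΔBP_ND as the percentage change from pre- to post-amphetamine BP_ND, and both passages fit that quantity.

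**Conclusion.** The gap is real, but it is one of interpretation. The alpha and power in Section V.12 are sound for a single region. They apply to Aim 1 or Aim 3 only if one region named in advance decides the aim, and none is named. Under an any-region rule, false support in the hypothesised direction is about 1.6 to 2.3 times the nominal 2.5% at correlations of 0.8 to 0.95 (4.0/2.5 to 5.8/2.5). Under an all-four rule, power stays below 0.80 at n=25 and reaches it at n=30 only at a correlation of about 0.9 or more.

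These sizes rest on equal inter-region correlation, an assumed range for it, d=0.59 in every region for the power figures, and an evaluable n of 25 that I inferred. That the tests are unadjusted, and that the power line concerns one region, are also inferences: the plan is silent on both.

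Two stronger readings should be resisted. The documents do not show that d′=0.59 is miscalculated, and they do not show that the study is too small. A stated rule is enough, and this is a cheap improvement to a preliminary study.

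**What to change.** Add to Section V.12, before unblinding:

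1. Name one primary region per cohort, chosen by the investigators, and state that it alone decides the aim. Test its relative change in BP_ND, calcitriol + Amp against placebo + Amp, at two-sided 0.05.
2. Treat the other three regions as secondary, with Holm adjustment across them, tested formally only if the primary region is significant. Report all four estimates with confidence intervals either way.
3. State that the power line refers to the primary region, and give the evaluable N it assumes.

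If the investigators want the four regions to stay co-equal, Holm over all four is an acceptable alternative. The chance of at least one positive region is then 0.98 to 0.70 at n=25 and 0.99 to 0.79 at n=30 as correlation rises from 0 to 0.95.

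The cost is wording only. The downside of the first option is that three regions become secondary, with average power per region of about 0.61 to 0.70 at n=25 and 0.74 to 0.79 at n=30.
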